6 STUDY INTERVENTION(S)

6.1 STUDY INTERVENTION(S)

[figure not shown]
6.1.1 DESCRIPTION OF CDS INTERVENTION

The PedsBP CDS will be integrated within the EHR (EPICare, Verona, WI) with data transfer to and from a web service, based at HP, for data processing. PedsBP CDS will be activated when a patient 6-17 years has a BP measured and entered in the vital sign section of the EHR during an ambulatory primary care visit in a randomized study clinic. Eligible patients will be allocated to the study arm assigned to their clinic at their index visit. Figure 2 illustrates how data would flow from the EHR to and from the HP-based web-service for the proposed study.

The PedsBP CDS tool includes seven key features:

- (i) a best practice advisory (BPA) regarding the need for height data to classify the BP by percentile
- (ii) a BPA to repeat any BP that is $\geq 95^{\text{th}}$ percentile or $\geq 130/80$ mm Hg
- (iii) classification of current and prior BPs in the prior two years and identification of BPs in stage 1 HTN and stage 2 HTN range
- (iv) review of previous HTN diagnoses and BPs in order to classify an elevated BP at the current or index visit as a first or second elevated BP, or as meeting criteria for HTN
- (v) review of medications and diagnoses that may affect BP
- (vi) tailored CDS based on HTN category and previous diagnoses
- (vii) graphical representation of current and prior BP data by age and BP percentile.

Figure 2. Peds & TeenBP CDS Data Capture

[figure not shown]

Each of these features is described below in Figure 3.

The first component of the CDS is a BPA to ensure a current height measurement for children 12 and under (needed to compute BP percentiles): (a) If a height is entered at the visit, it will be used; (b) If no height is entered when entering a BP, the closest antecedent height recorded within 1 year is used to calculate a BP percentile, assuming a constant height percentile. If there is no height available for the current visit or the prior 12 months, a BPA displays requesting a height be measured and recorded in the EHR. As height measurement is standard in pediatric care, this BPA is currently firing in less than 1% of visits.

The second component of the CDS, a BPA to repeat an elevated BP, is triggered for BPs $\geq 95^{\text{th}}$ percentile in children 6-12 years or $\geq 130/80$ mmHg in youth 13-17 years when the BP is entered into the vital signs section of the EHR, and the vital signs box is closed.

Figure 3. Example of Peds & TeenBP CDS for 6-year old meeting criteria for Stage 1 HTN

In the third component, the CDS will use the lowest SBP for that visit to assign BP percentiles and classify BPs as normotensive, elevated BP, stage 1 HTN, or stage 2 HTN. If the initial elevated BP is not repeated, the BP percentile will be calculated for the available measurements. BP percentiles are calculated as in Appendix B of the Fourth Report³⁶ and include the new reference population, as described in the 2017 Guidelines.⁹

In the fourth component of the CDS, for patients with BP $\geq 95^{\text{th}}$ percentile (6-12 years of age) or $\geq 130/80$ mmHg (13-17 years of age), the CDS reviews data pulled from the EHR including prior HTN diagnoses, prior BPs and heights. The index and previous BPs and diagnosis data are used to categorize elevated BPs as incident or persistent, and to determine whether a patient meets clinical criteria for new onset stage 1 or stage 2 HTN, or pre-existing HTN.

In the fifth component of the CDS, current medications (e.g., oral steroids or stimulants that increase BP or diuretics that lower BP) and prior diagnoses that may affect BP are displayed. In addition, current body mass index (BMI) and BMI percentile are calculated. For patients meeting criteria for obesity, BMI $\geq 95^{\text{th}}$ percentile with new onset HTN, obesity is noted in the CDS as a potential cause for the HTN.

In the sixth component of the CDS, providers receive tailored CDS for BPs $\geq 95^{\text{th}}$ percentile or $\geq 130/80$ mmHg. The CDS recommendations are specific, based on the magnitude of BP elevation (stage 1 or stage 2 HTN) and whether the BP is

incident or persistent. If the patient has a prior diagnosis of HTN, the CDS provides tailored feedback regarding whether the BP is at goal (<95th percentile) or elevated and possibly requires initiation or a change in medication.

In the seventh component of the CDS, current and previous SBPs and DBPs, within the last 2 years are graphed and displayed, with elevated BP, stage 1, and stage 2 HTN BP cutoffs specified. This feature allows providers to visualize patient-level variability and trends in BP over time. In addition, the CDS can be printed for families, to assist with shared decision making. An example, including the display of BPs over time, is shown in Figure 3.

6.2 RANDOMIZATION STRATEGY

Covariate-based constrained randomization⁹⁸ may be used to enhance study arm balance on key factors during randomization of the clinics in this cluster-randomized trial. This method permits the use of multiple balance factors and can yield improved study arm balance and increased statistical power beyond simple randomization when balance factors are included in both the design and analysis phase⁹⁹ of the study. Clinic-level attributes of clinics and patient mix to be used as balance factors will be obtained via EHR data and ascertained for care in clinics in the 18 months prior to randomization. Proposed clinic-level balance factors include baseline levels of BP re-measurement and HTN recognition, number of visits with patients age 6-17 (ranging from 145 to 6556 patients per clinic over 18 months in preparatory data), location (metropolitan/micropolitan (20 clinics) versus small town/rural (25 clinics)), and proportion of public pay patients (ranging from 13% to 73%). Randomization will be carried out with the CCR macro for use within SAS¹⁰⁰, and conducted one month prior to implementation of the low- and high-intensity strategies in clinics.

7 TRAINING REQUIREMENTS

7.1 OVERALL TRAINING APPROACH

Training for clinics in low- and high-intensity arms will be developed to incorporate general training, study-specific training, and mechanisms for competency assessment. The study team is responsible for the development of a comprehensive Training Plan, instructional material, and delivery of the training (e.g., via self-study, webinar, or teleconference). Within primary care clinics randomized to receive the PedsBP CDS, rooming teams will be trained on how to recognize the PedsBP alerts and may receive basic education on BP measurement and HTN; PCPs will be trained on how to use the PedsBP CDS. Training instructions will include how to let the study team know of any issues or questions. Traditionally, we have completed such trainings at in-person lunch meetings with clinic personnel, but will also consider other training modalities, such as web-based trainings or teleconferences, depending on the standard training practices and clinic leadership preference.

8 STATISTICAL CONSIDERATIONS

8.1 STATISTICAL HYPOTHESES

Specific Aim 1: Among youth 6-17 years with an elevated BP measurement ($\geq 95^{\text{th}}$ percentile or $\geq 130/80$ mmHg), to evaluate the effectiveness of the adapted PedsBP for repeat BP measurement:

Hypothesis 1: Youth with elevated BP measured at a PedsBP intervention clinic will be more likely to have a repeat BP

measurement during their visit as compared to those attending usual care clinics.

Hypothesis 2: Youth with elevated BP measured at a high-intensity PedsBP clinic will be more likely to have a repeat BP measurement during their visit, as compared to those attending low-intensity PedsBP clinics.

Specific Aim 2. Among youth 6-17 years meeting criteria for HTN, to evaluate the effectiveness of the adapted PedsBP for improving HTN recognition:

Hypothesis 3: Youth meeting criteria for HTN at a PedsBP intervention clinic will be more likely to be clinically recognized within 6 months of their index visit, as compared to those attending usual care clinics.

Hypothesis 4: Youth meeting criteria for HTN at a high-intensity PedsBP clinic will be more likely to be clinically recognized within 6 months of their index visit, as compared to those attending low-intensity PedsBP clinics.

Table 2. Study Contrasts and Outcomes by Hypothesis

Hypothesis	Contrast	Denominator	Outcome(s)	Data source(s)
H1	CDS (low- or high-intensity) versus Usual care	First BP at visit $\geq 95^{\text{th}}$ percentile (ages 6-12) or $\geq 130/80$ mmHg (ages 13-17)	Repeat BP measured and recorded at same visit	Automated BP data from EHR or CDS
H2	CDS low-intensity versus CDS high-intensity			
H3	CDS (low- or high-intensity) versus Usual care	BP at visit and at least 2 of 4 prior BPs, within last 2 years, $\geq 95^{\text{th}}$ (ages 6-12) or $\geq 130/80$ mmHg (ages 13-17)	HTN recognition within 6 months of meeting criteria for HTN	Automated data from EHR or CDS
H4	CDS low-intensity versus CDS high-intensity			
Secondary / Exploratory	CDS (low or high intensity) versus Usual care	BP at visit and at least 2 of 4 prior BPs, within last 2 years, $\geq 95^{\text{th}}$ (ages 6-12) or $\geq 130/80$ mmHg (ages 13-17)	Management within 6 months of meeting criteria for HTN including: Lifestyle counseling, Referrals, Medications for HTN, Diagnostic imaging / BP at 12 months Provider satisfaction	Automated data from EHR or CDS, limited chart review and provider survey

8.2 SAMPLE SIZE DETERMINATION

Aim 1. Preliminary data from EH indicate there were 44,061 unique patients age 6-17 with visits to the 45 largest EH primary care clinics in an 18-month period. This data also indicates that 16% (n=7,258) of patients age 6-17 years had an elevated BP at initial measurement and BP re-measurement occurred at 30% (n=2210) of encounters with an elevated BP. The initial PedsBP trial had a clinic-level ICC for BP re-measurement of 0.03 and BP re-measurement of 28% in UC and 47% in the PedsBP arm.²³ With an expected 7,258 patients (161 per clinic), this study has 99% power for the H1 comparison of low- plus high-intensity clinics (30 clinics) with 15 UC clinics (alpha=.05, two-sided test, ICC=0.03) to detect a raw BP re-measurement difference of 15% between the usual care arm (30%) vs. low- plus high-intensity arms (45%). The minimum detectable difference with 80% power is 8% (30% UC vs. 38% low- plus high-intensity arms). With an expected 4,840 patients (161 per clinic), this study has 80% power for the H2 comparison of low-intensity (15 clinics, 2420 patients) vs. high-intensity clinics (15 clinics, 2420 patients), with alpha=.05, two-sided tests, ICC=0.03, to

detect a minimum detectable difference in BP re-measurement of 10% between the low-intensity arm (40%) vs. the high-intensity arm (50%).

Aim 2. Based on the prior Peds & TeenBP trial²⁴, along with observational studies of pediatric HTN¹⁰⁻¹² we anticipate 2% of patients age 6-12 and 3% of patients age 13-17 will newly meet HTN criteria at a visit over 18 months, yielding a sample size of 1060 patients (24/clinic). The PedsBP study found that 21% of patients newly meeting HTN criteria were recognized over 6 months in UC and 55% in the PedsBP arm²⁴, and the clinic-level ICC for HTN recognition was 0.035. With 1060 patients (24/clinic) and 45 clinics, this study has 99% power (alpha=.05, two-sided test, ICC=0.035) for H3 to detect a difference in HTN recognition of 17% between UC (20%) and the low- plus high- intensity arms (37%), and a minimum detectable difference of 11% (20% UC vs. 31% low- plus high-intensity arms) at 80% power. For H4 the minimum detectable difference at 80% power for HTN recognition among 706 patients (24/clinic) is 14% between low-intensity (30%) and high-intensity (44%) arms. Power computations account for the design effect due to clinic randomization and unequal counts of clinics in some comparisons and were conducted with PASS 2019.

8.3 POPULATIONS FOR ANALYSES

We will continue to engage with EH leadership to ensure the active participation of EH clinics. EH leadership support for this project, as evidenced in the letters of support, ensures the participation of primary care clinics.

Patients 6 to 17 years of age with a BP recorded at a participating EH primary care clinic will be eligible and automatically enrolled on the basis of data recorded in the EHR and captured by the PedsBP CDS. Given that one of the primary purposes of the study is to test the effectiveness of the different intervention approaches, including a high-intensity intervention with additional outreach and engagement of clinicians and rooming staff, we do not plan to conduct additional recruitment or retention activities.

Aim 1 outcomes will be assessed in the context of care provided at the index visit with an isolated hypertensive BP recorded. Aim 2 outcomes will be assessed over a period of 6 months following when a patient meets criteria for HTN. Clinical recognition of HTN, dietitian or other lifestyle referral and lifestyle counseling will be assessed based on care received. There will be no additional efforts to recall patients for additional study visits. For subjects with no follow-up visits, Aim 2 outcomes will be assessed based on clinical actions at the index visit.

Providers and rooming staff will be invited to participate in surveys and in-depth interviews through email or in-person recruitment by EH study staff. Surveys and interviews will be conducted at the time of recruitment as well as through a follow-up survey at the end of the intervention period. We will work with clinic administrative staff as necessary to help coordinate interviews and surveys with clinicians and rooming staff in a way that is not disruptive to regular clinic operations.

Data sources

Data required for PedsBP CDS-enhanced care will be sent to HPI for PedsBP operations. CDS data is retained in the transactional data store with minimal access until needed for analysis. With respect to the transactional data store, the following measures will be taken to protect PCPs and patients from the risk of breach of confidentiality: A unique study ID code unrelated to the medical record number or other study subject-specific information will be assigned to each patient at the index visit (first visit in the intervention period). The study ID is used to link data from patient encounters over time and various data sources that are needed for analysis. All index and subsequent encounter data for eligible patients, including vitals, medications and diagnoses, are securely stored behind a firewall within a limited de-identified dataset.

A crosswalk table linking this code number to a medical record number or patient name will be created by EH programmers in order to 1) check against opt out lists, and 2) link to study outcomes. EIRH Informatics Analysts assigned to this research project will exclude patients who have opted out via general consent; data for these patients will not be stored in analytic data files. The data for patients who have opted out of external research will be deleted from analyses files. The crosswalk will be destroyed within 12 months after completion of the linked databases needed to test study hypotheses. This project will be governed by a Business Associates Agreement, DUA, and appropriate services agreements.

8.4 STATISTICAL ANALYSES

Aim 1. Preliminary data from EH indicate there were 44,061 unique patients age 6-17 with visits to the 45 largest EH primary care clinics in an 18-month period. This data also indicates that 16% (n=7,258) of patients age 6-17 years had an elevated BP at initial measurement and BP re-measurement occurred at 30% (n=2210) of encounters with an elevated BP. The initial Peds & TeenBP trial at HealthPartners had a clinic-level ICC for BP re-measurement of 0.03 and BP re-measurement of 28% in UC and 47% in the Peds & TeenBP arm.²³ With an expected 7,258 patients (161 per clinic), this study has 99% power for the H1 comparison of low- plus high-intensity clinics (30 clinics) with 15 UC clinics (alpha=.05, two-sided test, ICC=0.03) to detect a raw BP re-measurement difference of 15% between the usual care arm (30%) vs. low- plus high-intensity arms (45%). The minimum detectable difference with 80% power is 8% (30% UC vs. 38% low- plus high-intensity arms). With an expected 4,840 patients (161 per clinic), this study has 80% power for the H2 comparison of low-intensity (15 clinics, 2420 patients) vs. high-intensity clinics (15 clinics, 2420 patients), with alpha=.05, two-sided tests, ICC=0.03, to detect a minimum detectable difference in BP re-measurement of 10% between the low-intensity arm (40%) vs. the high-intensity arm (50%).

Aim 2. Based on the prior Peds & TeenBP trial²⁴, along with observational studies of pediatric HTN¹⁰⁻¹² we anticipate 2% of patients age 6-12 and 3% of patients age 13-17 will newly meet HTN criteria at a visit over 18 months, yielding a sample size of 1060 patients (24/clinic). The Peds & TeenBP study found that 21% of patients newly meeting HTN criteria were recognized over 6 months in UC and 55% in the Peds & TeenBP arm²⁴, and the clinic-level ICC for HTN recognition was 0.035. With 1060 patients (24/clinic) and 45 clinics, this study has 99% power (alpha=.05, two-sided test, ICC=0.035) for H3 to detect a difference in HTN recognition of 17% between UC (20%) and the low- plus high-intensity arms (37%), and a minimum detectable difference of 11% (20% UC vs. 31% low- plus high-intensity arms) at 80% power. For H4 the minimum detectable difference at 80% power for HTN recognition among 706 patients (24/clinic) is 14% between low-intensity (30%) and high-intensity (44%) arms. Power computations account for the design effect due to clinic randomization and unequal counts of clinics in some comparisons and were conducted with PASS 2019.

Hypotheses 1 and 2 for **Aim 1** posit that patients with an elevated BP seen at clinics with low- or high-intensity PedsBP CDS will be more likely to have their BP re-measured as compared to patients seen at usual care clinics, and that repeat measurement will be more likely for patients seen at high-intensity rather than low-intensity clinics. Because clinics are randomized and the outcome varies at the patient level, generalized linear mixed-model regression with a logit link and binomial error distribution will be used to test the effect of the interventions using the model specified below.

$$\text{Aim 1, H1: } \text{BP_Remeasure}_{ji} = \gamma_{00} + \gamma_{10}\text{TeenBP}_j + \gamma_{20}\text{StratFactors}_j + \gamma_{01}\text{PatientCovars}_i + [\text{u}_{j0} + \text{e}_{ji}]$$

$$\text{Aim 1, H2: } \text{BP_Remeasure}_{ji} = \gamma_{00} + \gamma_{10}\text{HighVsLow}_j + \gamma_{20}\text{StratFactors}_j + \gamma_{01}\text{PatientCovars}_i + [\text{u}_{j0} + \text{e}_{ji}]$$

The dependent variable for Aim 1 (BP_Remeasure) is a binary indicator of post-implementation re-measurement of BP at the index visit at which the elevated BP occurred. For H1 this endpoint will be predicted by a fixed effect study arm term (TeenBP_j) contrasting low- plus high-intensity PedsBP clinics with usual care clinics, stratification factors used in the clinic randomization (StratFactors_j), and patient-level covariates of age, sex, and SBP percentile of the elevated BP. A random intercept for clinics is included (u_{j0}) to account for the clinic-level randomization. The analysis for H2 will contrast high- and low-intensity clinics (HighVsLow_j) and exclude usual care clinics from the analysis, but otherwise be similar to H1. Statistically significant study arm contrasts (alpha=.05) and parameters in the expected direction will support the H1 and H2 predictions stated for Aim 1.

Hypotheses 3 and 4 for **Aim 2** posit that patients who newly meet HTN criteria at clinics with low- or high-intensity PedsBP CDS will be more likely to have their HTN recognized within 6 months as compared to patients seen at usual care clinics, and that recognition of HTN will be more likely for patients seen at high-intensity rather than low-intensity clinics. Generalized linear mixed-model regression with a logit link and binomial error distribution may be used to test the effect of the interventions following the same analytic strategy and equations for H1 and H3 above, with the substitution of HTN recognition as an endpoint in place of BP re-measurement, and the use of patient-level covariates of the lowest SBP percentile at the index visit, and BMI percentile at the index visit. Study arm contrasts will test differences in BP recognition for CDS (low-intensity or high-intensity) vs. Usual care and high-intensity vs. low-intensity. Statistically significant study arm contrasts (alpha=.05) and parameters in the expected direction will support the H3 and H4 predictions stated for Aim 2.

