1.1 SYNOPSIS

Title:	Improving Recognition and Management of Hypertension in Youth: Comparing Approaches for Extending Effective CDS for use in a Large Rural Health System
Grant Number:	AHRQ 1R18HS027402-01A1
Study Description:	This research project will adapt the PedsBP clinical decision support (CDS) tool for use at Essentia Health and measure the implementation processes and outcomes. This minimal risk, pragmatic trial will randomize up to 45 Essentia clinics in a 3-arm, cluster-randomized trial. Clinics will be randomly allocated in a 1:1:1 allocation ratio to usual care, low-intensity implementation, or high-intensity implementation of the PedsBP CDS. Study-eligible patients will be allocated to the study arm assigned to the clinic at which the patient has an index visit when blood pressure (BP) is measured. Clinic providers and rooming staff will be interviewed and surveyed to assess experience and satisfaction with the CDS.
Objectives:	Identify optimal intervention implementation strategies for the PedsBP CDS tool. Post-implementation comparisons of high- plus low-intensity implementation versus usual care and high- versus low-intensity implementation will be conducted for the primary endpoints of BP remeasurement at the index visit (for patients with an elevated first BP), and BP recognition within 6 months of the index visit (for patients newly meeting HTN criteria).
Endpoints:	There are two primary outcomes. One is repeat BP measurement during the same clinic visit, of an initial BP that is \geq 95th percentile for children 6-12 years or \geq 130/80 mmHg for adolescents 13-17 years. Repeat BPs can be measured by providers or rooming staff but will only contribute to this outcome if recorded in the vitals section of the EHR. The other primary outcome is clinical recognition of HTN within 6 months of meeting criteria for HTN. Clinical recognition will include a new diagnosis of HTN (ICD-10: I10) or elevated BP (ICD-10: R03), adding HTN or elevated BP to the problem list. Secondary outcomes will describe management within 6 months of meeting criteria for HTN including: lifestyle counseling, dietitian referrals, subspecialty referrals, initiation of antihypertensive medications and receipt of diagnostic imaging (echocardiogram or renal ultrasound). BP control at 12 months following the index date meeting criteria for HTN will be an exploratory outcome.

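### H1 codes the three randomised arms as one pooled CDS indicator, so a true high- versus low-intensity gap widens its standard error relative to a three-arm model (about 10% at a 10-point gap and ICC 0.03)

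*Combined protocol and SAP*

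**What the plan says.** The synopsis (section 1.1) has clinics "randomly allocated in a 1:1:1 allocation ratio to usual care, low-intensity implementation, or high-intensity implementation". In section 8.4, for Aim 1, "generalized linear mixed-model regression with a logit link and binomial error distribution will be used". The printed H1 equation has a single arm coefficient, and the text says the endpoint is "predicted by a fixed effect study arm term (TeenBP_j) contrasting low- plus high-intensity PedsBP clinics with usual care clinics". The clinic effect is one intercept: "A random intercept for clinics is included (u_{j0}) to account for the clinic-level randomization". Randomisation factors and patient covariates complete the model.

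The same section states as H2 "that repeat measurement will be more likely for patients seen at high-intensity rather than low-intensity clinics". H2 has its own model, which drops the usual care clinics. Its power statement uses 40% versus 50% as the difference detectable with 80% power.

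For Aim 2 the text points back to equations for H1 and H3, but only H1 and H2 are printed. It then says: "Study arm contrasts will test differences in BP recognition for CDS (low-intensity or high-intensity) vs. Usual care and high-intensity vs. low-intensity". No estimation method (ML, REML or quadrature) and no degrees-of-freedom rule is named for any of these models.

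**The concern.** With one binary arm term, low- and high-intensity clinics share one fitted mean. If their true rates differ, each CDS clinic departs from that mean by half the gap in addition to its own clinic effect. The random intercept absorbs this known, design-made difference as if it were chance variation between clinics.

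The H1 estimate hardly moves, because the two CDS arms have equal numbers of clinics. Its standard error grows. What is at stake is the width of the H1 interval and, for an effect near the detectable limit, some power. H2 and H4 use only the 30 CDS clinics with a high-versus-low term, so they are not touched.

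**Working it through.** **Inputs.** From sections 8.2 and 8.4: 15 clinics per arm, 161 patients per clinic, ICC 0.03, two-sided alpha 0.05, H1 rates 30% versus 45%, H1 minimum detectable difference (MDD) 8 points (30% versus 38%), H2 rates 40% versus 50%. The midpoint of 40% and 50% is the 45% used for H1. The 5-point gap and the splits around 38% are assumptions.

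**1. The plan's own figures.** Design effect = 1 + 160 × 0.03 = 5.8. Effective sizes are 15 × 161/5.8 = 416 and 30 × 161/5.8 = 833. A two-proportion normal calculation gives 99.9% power at 30% versus 45% (stated 99%) and 80.2% at 30% versus 38% (stated 80%). Both statements reproduce.

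**2. Closed form, no covariates.** The variance of a clinic proportion is p(1−p) × 5.8/161.
- Usual care 30%: 0.00757. Low 40%: 0.00865. High 50%: 0.00901. Mean s² = 0.00841.
- The pooled term leaves 30 CDS clinics each half a gap from their fitted mean, on 45 − 2 = 43 df. Added variance = 30 × (gap/2)²/43 = 30 × 0.0025/43 = 0.00174.
- SE ratio = √(1 + 0.00174/0.00841) = 1.099. On the risk-difference scale, √(0.00841 × (1/15 + 1/30)) = 0.0290 rises to 0.0319.
- At 42.5%/47.5%: s² = 0.00845, added variance 0.00044, ratio 1.026. At no gap: 1.000.

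**3. Dependence on ICC**, same formula with design effects 2.6, 5.8 and 9.0:

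| Gap | ICC 0.01 | ICC 0.03 | ICC 0.05 |
|---|---|---|---|
| 5 points | +5.6% | +2.6% | +1.7% |
| 10 points | +21% | +9.9% | +6.5% |

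**4. Logistic mixed model by simulation** (restricted pseudo-likelihood, five clinic-level covariates, t test on 38 df pooled and 37 df three-level, 20,000 replicates per cell; patient covariates not simulated):

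| Usual care/low/high, % | SE inflation | Power, pooled | Power, three-level |
|---|---|---|---|
| 30/45/45 | 0 | 99.9% | 99.9% |
| 30/42.5/47.5 | +2.7% | 99.9% | 99.9% |
| 30/40/50 | +10.3% | 99.8% | 99.9% |
| 30/38/38 | about 0 | 79.4% | 79.2% |
| 30/35.5/40.5 | +2.8% | 77.2% | 78.6% |
| 30/33/43 | +10.8% | 71.7% | 78.0% |

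Clinic-proportion runs for the last two rows gave 76.3% versus 77.9% and 70.8% versus 78.4%. With unequal clinic sizes (an assumed 45-fold range, the same set in each arm) the logistic runs gave 70.6% versus 71.9% and 64.7% versus 70.5%. If the balance factors explained half the clinic variance (an assumption), the inflation would be 4.5 to 4.8% at 5 points and 17 to 18% at 10.

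**5. Absolute coverage depends on the estimator.** Under the REML-type SE with clinic df, pooled coverage in the logistic runs is 95.6% at 5 points and 97.0% at 10, against 95.0% and 95.2% for the three-level model. Clinic-proportion runs with five covariates, an ML-type variance (residual sum of squares divided by 45) and Wald z give:
- about 8% null rejection for either model;
- pooled coverage of about 93.5% at 5 points and 95.3% at 10;
- three-level coverage of about 92% at both gaps.

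**The case against.** The strongest reply is that the pooled indicator is a legitimate specification. It matches H1 as put in the synopsis, the objectives, Table 2 and the power calculation, and the high-low difference has its own hypothesis and model. No planned conclusion changes: at 30% versus 45%, power is above 99% either way. The loss of 6 to 8 points needs 30/33/43%, which sets H1's MDD beside H2's MDD. The documents never make that pairing, and neither figure is a forecast. If low equals high, the plan's model is better by a hair. All of this stands, and it is why the point is minor.

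A reader might infer that the pooled model makes H1 safely conservative. The documents do not support that. They name neither estimator nor degrees of freedom, and step 5 shows under-coverage at a 5-point gap with ML and Wald z. Only the relative statement, wider than the three-level model's SE, holds generally.

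A reader might also infer that H1's type I error is at risk from pooling. It is not: under the null with equal arms there is no gap to absorb. The roughly 8% rejection under ML and Wald z arises from the estimator and affects both models alike.

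The ICC comes from an earlier trial in urban and suburban clinics of another health system, so the percentages should be read with the range in step 3.

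**Conclusion.** The concern holds as a modest, avoidable loss of precision relative to a three-level arm model. At ICC 0.03 the H1 standard error is about 10% wider at a 10-point gap (21% at ICC 0.01, 6.5% at 0.05), 2.5 to 3% wider at 5 points (5.6% and 1.7%), and no wider without a gap. At the planned effect only the interval width changes. Near the 8-point MDD, under a REML-type SE with clinic df, the loss is about 6 to 8 points of power at a 10-point gap and about 1.5 points at 5 points.

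The direction of the gap is hypothesised in H2; its size is unknown. It would be tempting to extend the point to H3 and to the management endpoints that follow H3 (section 8.4.1), but no H3 equation is printed and the Aim 2 sentence on study arm contrasts may already mean a three-level factor. If H3 does take the H1 form, the same formula with its planning inputs (24 per clinic, ICC 0.035, 20/30/44%) gives about 10.5% at 14 points, again an MDD.

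**What to change.** For H1, replace the single indicator with a three-level arm factor on all 45 clinics. Keep the balance factors, patient covariates and clinic random intercept, and test (low + high)/2 minus usual care. Section 6.2 lists the balance factors: "Proposed clinic-level balance factors include baseline levels of BP re-measurement and HTN recognition, number of visits with patients age 6-17", location and public-pay share.

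Make this change only together with a REML-type standard error and clinic-based degrees of freedom (45 minus the number of clinic-level parameters). Under ML with Wald z the three-level model alone would lower coverage to about 92%. State in one sentence whether H3 uses the same form. Leave H2 and H4 as they are.

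The cost is one equation and a sentence or two in section 8.4, with no new data. It takes one clinic-level degree of freedom (38 to 37 if five balance factors enter singly) and 0.1 to 0.2 points of power if low equals high (79.4% to 79.2%; 72.7% to 72.5% with unequal sizes). Equal weighting of the two arms moves the estimate slightly: 0.664 to 0.662 log-odds at 30/40/50%, and under 1% in all runs. Those runs used the same set of clinic sizes in each arm, which randomisation does not guarantee.

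The intervention period was planned to end in January 2024 and the last logged amendment dates from March 2025. The documents do not say whether H1 has been analysed. If it has, keep the prespecified model as primary and report the three-level model as a sensitivity analysis.
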